7.1.4. Vital Signs and Physical Examination

Patients will have a physical examination to include weight, vital signs, assessment of ECOG performance status and height; height will be measured at Screening only.

7.1.5. (12-Lead) Electrocardiogram

Electrocardiogram (ECG): The Screening ECG will be a single 12-lead ECG. Triplicate 12-lead (with a 10-second rhythm strip) tracing will be used for all other ECGs. It is preferable that the machine used has a capacity to calculate the standard intervals automatically. At each time point (see the Schedule of Activities), 3 consecutive ECGs will be performed at approximately 2 minutes apart to determine the mean QTcF interval. If the mean QTcF is prolonged (>500 msec, ie, CTCAE Grade ≥3), then the ECGs should be re-evaluated by a qualified person at the site for confirmation as soon as the finding is made, including verification that the machine reading is accurate.

If manual reading verifies a QTcF of >500 msec, immediate correction for reversible causes (including electrolyte abnormalities, hypoxia and concomitant medications for drugs with the potential to prolong the QTcF interval) should be performed.

In addition, repeat ECGs should be immediately performed hourly for at least 3 hours until the QTcF interval falls below 501 msec. If QTcF interval reverts to less than 501 msec, and in the judgment of the investigator(s) and sponsor is determined to be due to cause(s) other than investigational product, treatment may be continued with regular ECG monitoring. If in that timeframe the QTcF intervals rise above 500 msec the investigational product will be

held until the QTcF interval decreases to 500 msec. Patients will then restart the investigational product at the next lowest dose level.

If the QTcF interval has still not decreased to 500 msec after 2 weeks, or if at any time a patient has a QTcF interval >515 msec or becomes symptomatic, the patient will be removed from the study. Additional triplicate ECGs may be performed as clinically indicated.

Prior to concluding that an episode of prolongation of the QTcF interval is due to investigational product, thorough consideration should be given to potential precipitating factors (eg, change in patient clinical condition, effect of concurrent medication, electrolyte disturbance) and possible evaluation by specialist.

If a patient experiences a cardiac or neurologic AE (specifically syncope, dizziness, seizures, or stroke), then an ECG (triplicate) should be obtained at the time of the event.

When matched with PK sampling, plan the timing of ECG accordingly so that the PK collection afterwards can be around the intended time point.

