1.5.2. Rationale for Safety Monitoring Plan

1.5.2.1. Cardiac Disorders

Valvulopathy – Inhibition of the TGFβ pathways was associated in galunasertib nonclinical studies with a number of cardiac toxicities that were characterized by aneurysms and valvulopathy with associated degenerative and inflammatory changes.⁵⁰ CCl

In addition, only patients with stable cardiac disease will be enrolled and monitored with periodic assessments of vital signs, electrocardiograms (ECGs), cardiac biomarkers (troponin, high-sensitivity C-reactive protein [hs-CRP], brain natriuretic peptide [BNP]), and Doppler echocardiography. Patients with any Grade 3 treatment-related cardiac event will be discontinued from the trial.

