1.5.2.3. Metabolism and Nutrition Disorders

Hypophosphatemia – Decreased serum phosphate was observed in the PF-06952229 nonclinical toxicology studies. The relevance of this finding in adults is unclear and substantive changes in serum phosphorus are not anticipated in the population to be enrolled in this clinical trial. Nevertheless, to mitigate any potential risk, serum phosphate will be included with requisite serum chemistry monitoring and regularly assessed throughout the study. Any confirmed treatment-related Grade 3 hypophosphatemia that does not resolve to baseline will result in dose modification or discontinuation from the trial.

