5.4.4. Recommended Dose Modifications

Dose modifications for enzalutamide due to toxicity or intolerable side effects are described in Sections 5.4.5 and Section 5.4.6.

Every effort should be made to administer PF-06952229 on the planned dose schedule (28-day cycle, 7 days on/7 days off).

In the event of significant toxicity, dosing may be delayed and/or reduced as described below. In the event of multiple toxicities, dose modifications should be based on the worst

toxicity observed. Patients are to be instructed to notify investigators at the first occurrence of any adverse symptom.

- No dose adjustments or reductions are allowed and patients are to discontinue the study treatment at any signs of medically significant cardiac toxicity.
- Patients will continue to receive the reduced dose as a result of AEs even after toxicity recovery.
- Patients who experience a second discreet DLT-equivalent toxicity will be discontinued from the study unless they are expected to continue to receive clinical benefit after discussion with the sponsor medical monitor or designee.
- Despite dose reductions or delays of PF-06952229 the patient will retain the same 28-day cycle of 7 days on and 7 days off. Note: If a treatment interruption continues beyond Day 28 of the current cycle, then the day when treatment is restarted will be counted as Day 1 of the next cycle.
- In the case where a patient is at a dose level deemed to be above a safe level (MTD determined below this dose level) discussion between the Investigator and the sponsor to determine what is in the best interest of the patient.

Dose modifications may occur in one of three ways:

- Within a cycle: dosing interruption until adequate recovery, and if required, dose reduction during a given treatment cycle;
- Between cycles: next cycle administration may be delayed due to persisting toxicity when a new cycle is due to start;
- In the next cycle: dose reduction may be required in a subsequent cycle based on toxicity experienced in the previous cycle.

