Serum bilirubin (Guidance for non-Gilbert's Syndrome patients. Agreement between sponsor and investigator is required for these patients).	Continue at the same dose level	Continue at the same dose level	When serum bilirubin ≥2 x ULN: Hold administration until recovery to Grade 0-1 within 2 weeks, serum bilirubin <2 xULN or baseline and reduce by 1 dose level. Discontinue dose if dose delay is more than 2 weeks.* If toxicity reoccurs despite reduction, patient may be dose reduced again by another dose level upon recovery to Grade 0-1 or baseline within 2 weeks unless the patient is in the first dose group, then only 1 dose reduction is allowed. Prompt palliative measures are strongly encouraged (eg, anti-emetics).	Patients who experience related Grade 4 non- hematologic toxicities despite optimal medical intervention should be discontinued from the study. *
Thrombocytopenia	Continue at the same dose level.	Continue at the same dose level.	Hold PF-06952229 until platelets ≥75,000/mm3. For platelet counts 10,000 – 25,000/mm³, continue monitoring every 3 days until recovery to ≥25,000/mm3 (Grade 3 or less) within 2 weeks. For platelet counts ≤10,000/mm3 monitor daily until recovery to ≥25,000/mm3 (Grade 3 or less) within 2 weeks. Reduce PF-06952229 by 1 dose level. If toxicity reoccurs despite dose reduction, patient may either be held until recovery within 2 weeks and continuation at same dose, or undergo further dose reduction by another dose	Consider Permanent discontinuation of study drugs for related Grade 4 AEs of any duration.

 Table 3.
 Dose Modifications for PF-06952229 - Related Toxicity

Toxicity	Grade 1	Grade 2	Grade 3	Grade 4
			level unless the patient is in the first dose group, then only 1 dose reduction is allowed.	
Non-hematologic	Continue at the same dose level.	Continue at the same dose level.	Withhold dose until toxicity is Grade ≤1, or has returned to baseline, within 2 weeks then resume treatment at the same dose level or reduce the dose by 1 level at the discretion of the investigator.*	Permanent discontinuation of study drugs for related Grade 4 AEs of any duration. * (Exclusion to this discontinuation for emesis, and clinically insignificant laboratory abnormalities that resolve within two days on optimum treatment, additional exclusions will require agreement between the investigator and sponsor).

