5.4.8. Study Stopping Rules and Patient Discontinuation

If the incidence of all bleeding events (all Grades) that are related to PF-06952229 is observed above 25%, the trial will be suspended.

All Grade 3 or Grade 4 bleeding events that are related to PF-06952229 will result in trial discontinuation for any patient who experience such clinical findings.

Any subsequent Grade 3 or Grade 4 bleeding event that is related to PF-06952229 will trigger a full review of overall safety of PF-06952229 and an assessment of the benefit/risks of this molecule in the studied patient population.

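### Four toxicity rules remove patients from the study or trial, where Section 6.4 and parallel rules stop treatment only; read literally, this could cost survival calls and some confirming scans in Part 2

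*Protocol*

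**What the plan says.** Four operative toxicity rules in the protocol end participation in the study or trial:

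- **7.1.5 (QTcF).** If QTcF has not come down to 500 msec after 2 weeks, exceeds 515 msec at any time, or the patient "becomes symptomatic, the patient will be removed from the study".
- **5.4.8 (bleeding).** Related Grade 3 or 4 bleeding "will result in trial discontinuation for any patient who experience such clinical findings".
- **5.4.4 (second DLT-equivalent).** "Patients who experience a second discreet DLT-equivalent toxicity will be discontinued from the study", unless clinical benefit is expected.
- **Table 3 in 5.4.7 (bilirubin row, Grade 4 cell).** Patients with related Grade 4 non-hematologic toxicity "despite optimal medical intervention should be discontinued from the study", with a footnoted clinical-benefit exception.

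Two rationale sentences echo them. Section 1.5.2.1 says "Patients with any Grade 3 treatment-related cardiac event will be discontinued from the trial". Section 1.5.2.3 says that confirmed, related, unresolved Grade 3 hypophosphatemia "will result in dose modification or discontinuation from the trial".

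Section 6.4 is built differently. It lists unacceptable toxicity among the reasons for stopping treatment and states that stopping treatment is not leaving the study. Its separate list of reasons for leaving the study does not name toxicity. Survival calls every 8 weeks run to study end. Section 7.8 continues scans after treatment stops.

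**The concern.** A site that meets one of the four triggers finds an instruction to end study participation in one place and an instruction to keep following the patient in another. If it follows the first, two Part 2 secondary results are exposed:

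- **OS.** Survival calls would stop. SAP 6.3.1 censors OS at the last visit, so the patient would be censored early for a reason tied to toxicity. That loss may not be independent of prognosis.
- **Confirmed ORR.** The Schedule of Activities ends tumor assessments when a patient leaves the study altogether. A responder removed soon after the first response scan could miss the second one. SAP Section 6 keeps an unconfirmed responder in the denominator of confirmed ORR and out of the numerator.

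**Working it through.** **1. The rules side by side.**

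| Event | Study or trial wording | Treatment-only wording |
|---|---|---|
| Related Grade 4 non-hematologic toxicity | Table 3, bilirubin row | Table 3, non-hematologic row: "Permanent discontinuation of study drugs for related Grade 4 AEs of any duration" |
| Cardiac | 7.1.5 (QTcF); 1.5.2.1 (rationale) | 5.4.4 and Table 4: "patients are to discontinue the study treatment at any signs of medically significant cardiac toxicity" |
| Bleeding | 5.4.8 | 7.8: hemorrhage found on imaging stops drug and moves the patient to follow-up |
| Second DLT-equivalent | 5.4.4 | None; the conflict is with 6.4 alone |

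One Grade 4 event can therefore receive two different instructions within Table 3.

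**2. What is not exposed.**
- PFS, duration of response and time to progression: SAP 9.2 already censors these at discontinuation for toxicity.
- AE and SAE collection: 8.1.4 ties it to the last dose (at least 28 days).
- PSA50: the last scheduled PSA is at End of Treatment under either reading.
- Unconfirmed ORR: SAP Section 6 reports it alongside confirmed ORR.

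**3. How often the triggers might fire.** The only data are from Part 1A (Appendix 10, to 19 June 2020).
- Enrolled before the July 2019 hold: 4 + 6 + 3 = 13. Enrolled after it: 20 − 13 = 7.
- Related Grade 3 bleeds before the hold: 2/13 = 15.4% (exact 95% CI 1.9% to 45.4%). After it: 0/7 (0% to 41.0%).
- Related Grade 4 AEs: 0/20 (0% to 16.8%).

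Appendix 10 gives no count for the QTcF or second-DLT triggers. For assumed combined rates of 0%, 1%, 5% and 10%, the expected number among the 10 + 20 = 30 Part 2 patients is 0, 0.3, 1.5 and 3.

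**4. Size for OS.** Suppose one of N patients is lost before the first death, and the Kaplan-Meier value S at some later time is 50% (assumed). With the lost patient's status unknown, the full-cohort proportion lies between (N − 1)/N × S and (N − 1)/N × S + 1/N.
- Part 2B, N = 20: 0.95 × 0.5 = 47.5%, to 47.5% + 5% = 52.5%. Standard error √(0.25/20) = 11.2 points.
- Part 2A, N = 10: 0.9 × 0.5 = 45%, to 45% + 10% = 55%. Standard error √(0.25/10) = 15.8 points.

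The shift is at most 2.5 or 5 points, well inside one standard error.

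For the last patient enrolled, assume removal at week 8 and survival to week 104. The follow-up visit falls at week 12 or 13, so calls would run at weeks 20 to 100 or 21 to 101: (100 − 20)/8 + 1 = 11 calls lost. Earlier enrollees could lose more, because study end is counted from the last patient's first treatment.

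**5. Size for confirmed ORR.** The Part 2B example in 9.6.2 is 7/16 = 43.75%. With one confirmation lost it is 6/16 = 37.5%, a drop of 1/16 = 6.25 points.

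**The case against.** The strongest reply is that context settles the wording. Sections 5.4.4 and Table 3 are dose-modification rules whose clinical-benefit exceptions make sense only if study means drug. Section 3.2 and the Table 3 footnote use the word that way. The QTcF sentence closes a hold-and-restart sequence for the investigational product. This stands, and the probable intent is to stop the drug.

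Section 7.8 also calls for assessments after end of treatment unless the patient stopped for progression, death or withdrawal of consent, so patients stopped for toxicity are covered. The Schedule's examples of leaving the study do not name toxicity, and 7.8 says confirmation of response is only preferred. Section 6.4 continues survival follow-up even when a patient refuses visits, and it points to public sources for vital status. All of this reduces the risk. The public-source provisions, however, are written for patients who withdraw consent or cannot be reached, not for a patient whom a protocol rule removes.

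Three stronger readings are tempting and fail:

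- A reader might infer that 6.4 itself authorizes removal from the study for safety. That sentence opens with withdrawal from treatment, which most naturally governs the whole of it. Section 8.1.3, despite its title, is a recording rule.
- A reader might infer a fixed exposed period between scans. None can be derived. The End of Treatment visit may fall up to 4 weeks after the last dose, and the documents give both a 6-week (7.8) and an 8-week (Schedule) test for repeating the scan.
- A reader might take 2/13 as the expected bleeding rate in Part 2. Those events predate the tightened entry criteria.

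**Conclusion.** The concern holds as a minor inconsistency. Four operative rules say study or trial where 6.4, and for three of them a parallel rule, stop treatment only. The harm requires a site to follow the literal words over 6.4 and 7.8. It is confined to OS and confirmed ORR in Part 2, the number of patients affected cannot be derived, and it may be zero. If one patient were affected, confirmed ORR in the Part 2B example would fall by 6.25 points, and OS would move by at most 2.5 points (Part 2B) or 5 points (Part 2A) at an assumed 50%. The trigger rates, the 50% and the week-8 removal are assumptions. The SAP states no hypotheses, and no conclusion of the trial depends on this point.

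**What to change.** In 7.1.5, 5.4.8, 5.4.4 (second DLT-equivalent) and the Grade 4 cell of the Table 3 bilirubin row, write: *permanently discontinued from study treatment and entered into follow-up (Section 6.4)*. Sections 5.4.7 and 5.7 already use this form. Conform the rationale in 1.5.2.1 in the same way, and in 1.5.2.3 write: *dose modification or permanent discontinuation of study treatment*.

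Leave every trigger and clinical-benefit exception as it is. Do not reword the 6.4 withdrawal sentence, because it also covers behavioral reasons and inability to comply. At most, retitle 8.1.3 and the cross-reference to it so that they refer to discontinuing treatment.

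The cost is four operative edits and two rationale edits in the next amendment, plus completing follow-up that is already scheduled.

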7.2. Echocardiogram

Echocardiogram (Echo) will be evaluated in all patients. The following parameters will be evaluated: ventricular function (including left ventricular ejection fraction [LVEF], end systolic volume [ESV] and end diastolic volume [EDV]), qualitative evaluation of chamber size, and wall motion. A Doppler examination will be completed and should include an assessment of mitral valve, atria, right ventricle, tricuspid valve, aortic valve, pulmonic valve, great vessels, and pericardium. Additional assessments will be per the study manual.

7.3. Pharmacokinetics Assessments

7.3.1. Plasma for PK analysis of PF-06952229

Blood samples (3 mL) to provide a minimum of 1.2 mL plasma for PK analysis will be collected into appropriately labeled tubes containing dipotassium ethylenediaminetetraacetic acid (K₂EDTA) as outlined in the Schedule of Activities. The PK sampling schedule may be modified based on emerging PK data.

In addition to samples collected at the scheduled times, an additional blood sample should be collected from patients experiencing unexpected and/or serious AEs and the date and time of blood sample collection and of last dosing prior to PK collection documented on the CRF.

Where noted in the Schedule of Activities, blood samples for PF-06952229 concentrations will be collected at approximately the same time as other assessments such as

CCI

, ECGs (first ECG then PK collection) and bone marrow aspirate collections etc, wherever possible.

All efforts will be made to obtain the PK samples at the scheduled nominal time relative to dosing. The exact time of the sample collection will always be noted on the CRF. If a

scheduled blood sample collection cannot be completed for any reason, the missed sample time may be re-scheduled with agreement of the clinical investigator, patient, and sponsor.

PK samples will be assayed for PF-06952229 using a validated analytical method.

The PK samples must be processed and shipped as indicated in the instructions provided to the investigator site to maintain sample integrity. Any deviations from the PK sample handling procedure (eg, sample collection and processing steps, interim storage or shipping conditions), including any actions taken, must be documented and reported to the sponsor. On a case-by-case basis, the sponsor may make a determination as to whether sample integrity has been compromised. Any deviation from the specified sample handling procedure resulting in compromised sample integrity will be considered a protocol deviation.

As part of understanding the PK of the investigational product, samples may be used for metabolite identification and/or evaluation of the bioanalytical method, as well as for other internal exploratory purposes. These data will not be included in the Clinical Study Report (CSR).

7.3.2. Urine for Analysis of PF-06952229 Concentrations

In single agent dose expansion cohort (Part 2A), optional urine samples will be collected for 12 hours (-3 hour window) after PF-06952229 morning dosing on Cycle 1, Day 7 to measure PF-06952229 concentrations, and thereby determine the renal elimination of PF-06952229 from the body. Urine will be collected on Cycle 1, Day 7 from selected patients over the following intervals: 0 to 4 hours, 4 to 8 hours, and 8 to 12 (-3 hour window) hours post the morning dose. Patients will empty their bladder just prior to morning dosing on Cycle 1, Day 7.

At the end of each urine collection period, the total volume will be measured and recorded. Voided urine should be collected in a container. The urine will then be mixed thoroughly, and an aliquot will be withdrawn for the potential measurement of drug concentrations. The sample must be processed and shipped as indicated in the instructions provided by the sponsor. The urine samples will be assayed using a validated analytical method in compliance with Pfizer SOPs.

Samples collected for analyses of urine PF-06952229 concentration may also be used for metabolite identification and/or evaluation of the bioanalytical method, or for other internal exploratory purposes. These data will not be included in the CSR.

7.6. Additional Research

Unless prohibited by local regulations or IRB/EC decision, patients will be asked to indicate on the consent form whether they will allow their banked samples to also be used to design and conduct research in order to gain a further understanding of other diseases and to advance science, including development of other medicines for patients.

Patients need not provide additional biospecimens for the uses described in this section;

Patients may still participate in the study if they elect not to allow their banked biospecimens to be used for the additional purposes described in this section.

Details on processes for collection and shipment of these samples can be found in the Lab Manual.

7.7. Imaging Assessments

Management of Incidental Findings

An incidental finding is one unknown to the patient that has potential health or reproductive importance, which is discovered unexpectedly in the course of a research study, but is unrelated to the purpose and beyond the aims of the study.

CT, MRI, and PET images may be reviewed by a central review facility. The purpose of this review is to evaluate images for response. Central image review is not a complete medical review of the patient. If, during the central review process, an unexpected observation is identified and this finding could, in the opinion of the central reviewer, have a significant health or reproductive consequence, this finding may be shared with the study sponsor for disclosure to the principal investigator. All follow-up testing and final diagnosis will be left to the discretion of the medical professionals at the site or those with an existing physician-patient relationship. The principal investigator will be responsible for reporting any AEs identified from incidental findings as described in the Adverse Event Reporting section. Identification of such incidental findings during the central review process should not be expected, and the site maintains responsibility for performing a general safety review of all images as per site protocols.

mCRPC Only: For mCRPC, prostate specific antigen (PSA) assessment should also be performed on Screening (for historical progression), C1D1 (-14 days) and Day 1 of Cycles 4, 7, 10 and every 2nd cycle thereafter as well as the End of Treatment visit, and should be evaluated using Prostate Working Group 3 – Soft Tissue Response Criteria. Patients should have a confirmatory scan for PD and should remain on trial if they are receiving clinical benefit (according to discussion with site investigator and sponsor).

Confirmation of response (CR/PR) with a second consecutive scan at least 4 weeks later is preferred. Tumor assessments should be repeated at the End of Treatment visit if more than 6 weeks have passed since the last evaluation. CT or MRI scans should be completed before tumor biopsy samples are collected. If a patient is classified as having progressive disease (PD) at a post-baseline tumor assessment, then confirmation of PD by a second consecutive scan at least 4 weeks later in the absence of rapid clinical deterioration is required.

Radiographic assessments obtained per the patient's standard of care prior to enrollment into the study do not need to be repeated and are acceptable to be used as baseline evaluation, if, (1) obtained within 28 days before C1D1 (standard of care imaging may be utilized prior to the 28 days after agreement between the sponsor and investigator), (2) performed using the method requirements (ie, RECIST v. 1.1), (3) the same technique/modality can be used to follow identified lesions throughout the trial for a given patient, and (4) appropriate documentation indicating that these radiographic tumor assessments were performed as standard of care is available in the patient's source notes. All patients' files and radiologic images must be available for source verification and for potential peer review. All study images may also be provided by the study site to an independent radiology facility (IRF) for independent evaluation. Analysis of tumor assessments for the purpose of this study will be by investigator assessments and will be collected on CRFs.

Bone scans must be acquired on all patients using Tc99- methylene diphosphonate (MDP) tracer at screening and at subsequent post-baseline tumor assessments.

